		 Mesh exposure and erosion (ICD9/10 629.31, 629.32/T83.711, T83.721) Urinary Retention (CPT Code 53500, ICD 9/10 788.20, 788.21/R33.0, R33.8-R33.9) Urgency of urination (ICD9/10 788.63/R39.15) Urge incontinence (ICD9/10 788.31/N39.41) Bowel injury (ICD9/10 569.83/S36) Bladder/urethral injury (ICD9/10 596.6,867.0/S37) Infection (ICD9/10 686.9,998.5,999.3,998.51,998.59/T81) Retropubic hematoma (ICD 9/10 568.81,,568.81,459.0/K66.1) Retopubic hematoma (ICD 9/10 568.81,,568.81,459.0/K66.1) Retopubic hematoma (ICD 9/10 568.81,568.81,459.0/K66.1) Bulking Injection CPT 51715, ICD 9/10 59.72/ PCS 3E0K3GC Laparoscopic Retropubic Urethropexy CPT 51990, 51992, 51999 Abdominal Retropubic Urethropexy CPT 51840,51841 Needle Bladder Neck Suspension CPT 51845 Kelly plication CPT 57220 Cystourethroplasty CPT 51800 Subtypes: Stress incontinence, female/mixed incontinence (ICD9/10 625.6,788.33/N39.46) Stress incontinence (female) (male)(ICD10 CM N39.3) 		
Outcome	Mesh Removal	 General, CPT 57287-Removal or revision of sling for stress incontinence (fascia or synthetic) ***some erosions managed surgically may have been coded by a different CPT (i.e. 57295 revise vaginal graft via vaginal approach) and not CPT 57287, which indicates a sling revision/removal. 	Yes	Possible Options: (a surgery for any kind of mid-urethral sling, urethral bulking agent, black neck pubovaginal sling (autologous or allograft), or revision for mesh exposure). Represented as a Date, allows time-to-event analysis.
Outcome	Post-Procedural Pain	?, mix of vital sign (pain score >3 of 10 on vital sign data) and likely free text. Also, diagnosis codes related to abd/pelvic pain (if prior pain free).	Some portion	Would have to exclude prior chronic pain or detect specific mention of new pain (free text). Could analyze group with no pre-surgical pain,

Protocol 1				[15 July 2020]
				otherwise probably beyond scope. Date/Time of first post- op occurrence.

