		N39.498 Other specified urinary incontinence		
		Prolapse		
		ICD 9:		
		618.01 Cystocele, midline		
		618.02 Cystocele, lateral		
		618.03 Urethrocele		
		618.81 Incompetence or weakening of		
		pubocervical fascia		
		618.1 Uterine prolapse without mention of		
		vaginal wall prolapse		
		618.2 Uterovaginal prolapse, incomplete		
		618.3 Uterovaginal prolapse, complete		
		618.4 Uterovaginal prolapse, unspecified		
		618.5 Prolapse of vaginal vault after		
		hysterectomy		
		618.6 Vaginal enterocele, congenital or acquired		
		618.84 Cervical stump prolapse		
		618.04 Rectocele		
		618.05 Perineocele		
		618.82 Incompetence or weakening of		
		rectovaginal fascia		
		618.00 Unspecified prolapse of vaginal walls		
		618.09 Other prolapse of the vaginal walls		
		without mention of uterine prolapse		
		618.7 Old laceration of muscles of pelvic floor		
		618.83 Pelvic muscle wasting		
		618.89 Other specified genital prolapse		
		618.9 Unspecified genital prolapse		
		ICD-10 CM :		
		N81.0 Urethrocele		
		N81.10 Cystocele, unspecified		
		N81.11 Cystocele, midline		
		N81.12 Cystocele, lateral		
		N81.2 Incomplete uterovaginal prolapse		
		N81.3 Complete uterovaginal prolapse		
		N81.4 Uterovaginal prolapse, unspecified		
		N81.5 Vaginal enterocele		
		N81.5 Vaginal enterocele		
		N81.89 Other female genital prolapse		
		N99.3 Prolapse of vaginal vault after		
	1	1953.5 I TOTAPSE OF VAGITAL VAULT ALLEL	1	1
		hysterectomy		
		hysterectomy		
Exposure	SUI with Mesh	Admin Codes CPT 57288	Yes	Capture as date/time

Version 2.0 [15 July 2020]

Protocol 1				[15 July 2020]
Exposure	SUI without Mesh	Admin Codes	Yes	Capture as date/time
	IVIES11	CPT/ICD-9-CM/ICD-10-PCS 51715/ 59.72/3E0K3GC, 3E0K4GC Injection of implant into the urethra and/or bladder neck (collagen implant)		
		CPT/ICD-9-CM/ICD-10-PCS 51990, 51992/59.5/OTSD0ZZ, OTSD4ZZ Laparoscopic urethral suspension, laproscopic sling procedure		
		CPT/ ICD-9-CM/ICD-10-PCS 51841, 51840/ 59.5/0TSD0ZZ, 0TSD4ZZ Anterior vesicourethropexy, or urethropexy (eg, Marshall- Marchetti-Krantz, Burch)		
		CPT/ICD-9-CM/ICD-10-PCS 51845/59.5/0TSD0ZZ, 0TSD4ZZ Abdominovaginal vesical neck suspension		
		CPT /ICD-9-CM/ICD-10-PCS 57220/ 59.3/0TSC0ZZ, 0TSC4ZZ Kelly plication of urethrovesical		

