	788.39/N39.4 Other urinary incontinence
Prolapse	618.01/N81.11 Cystocele, midline
	618.02/N81.12 Cystocele, lateral
	618.03/N81.0 Urethrocele
	618.81/N81.82 Incompetence or weakening of pubocervical fascia
	618.1 Uterine prolapse without mention of vaginal wall prolapse
	618.2/N81.2 Uterovaginal prolapse, incomplete
	618.3/N81.3 Uterovaginal prolapse, complete
	618.4/N81.4 Uterovaginal prolapse, unspecified
	618.5/N99.3 Prolapse of vaginal vault after hysterectomy
	618.6/N81.5 Vaginal enterocele, congenital or acquired
	618.94/N81.85 Cervical stump prolapse
	618.04/N81.6 Rectocele
	618.05/N81.81 Perineocele
	618.82/N81.83 Incompetence or weakening of rectovaginal fascia
	618.00/N81.4Unspecified prolapse of vaginal walls
	618.09/N81.89 Other prolapse of the vaginal walls without mention of utering
	prolapse

	618.7/N88.1 Old laceration of muscles of pelvic floor
	618.83/N81.84 Pelvic muscle wasting
	618.89/N81.89 Other specified genital prolapse
	618.9/N81.9 Unspecified genital prolapse
Surgical Complications	629.31/T83.711 Erosion of implanted vaginal mesh
	629.32/T83.721 Exposure of implanted vaginal mesh
	996.76/T83.9 Complication of genitourinary device, implant or graft
	V58.2 Blood transfusion
	998.5 Postoperative infection
	778.2/R33.9 Urinary retention

Procedures

SUI Procedures – Sling	59.4/ OTSC4ZZ Suprapubic sling operation 59.79/ OTQD3ZZ Pubovaginal sling; Anterior urethropexy; Repair of stress incontinence NOS
SUI Procedures - Burch	59.5/ 0TSD4ZZ, 0TSD0ZZ Retropubic urethral suspension (Burch)
SUI Procedures - Other	59.6/ OTSC4ZZ, OTSCOZZ Paraurethral suspension
Soff foreduces of the	59.71/ OTUCOKZ Levator muscle operation for urethrovesical suspension
	59.72/ 3E0K4GC Injection of implant into urethra and/or bladder neck
Anterior Repair	70.51/ 0JQC0ZZ, 0JQC3ZZ Repair of cystocele
	70.54/ 0JUC07Z, 0JUC0JZ, 0JUC0KZ, 0JUC37Z, 0JUC3JZ, 0JUC3KZ Repair of
	cystocele with graft or prosthesis
Posterior Repair	70.52/ 0JQC0ZZ, 0JQC3ZZ Repair of rectocele

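### The Re-Operation row omits ICD procedure codes that the SUI-without-mesh row accepts for the same operations, so repeat operations recorded only by those codes are not counted

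*Protocol*

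**What the plan says.** The exposure row for SUI surgery without mesh (Section 13, data collection table) gives every operation codes from three systems:

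- Bulking: "CPT/ICD-9-CM/ICD-10-PCS 51715/ 59.72/3E0K3GC, 3E0K4GC Injection of implant into the urethra and/or bladder neck (collagen implant".
- Laparoscopic suspension: "51990, 51992/59.5/OTSD0ZZ, OTSD4ZZ Laparoscopic urethral suspension".
- Open urethropexy: "51841, 51840/ 59.5/0TSD0ZZ, 0TSD4ZZ Anterior vesicourethropexy, or urethropexy".
- Vesical neck suspension: "51845/59.5/0TSD0ZZ, 0TSD4ZZ Abdominovaginal vesical neck suspension".
- Kelly plication: CPT 57220, ICD-9 59.3, ICD-10-PCS 0TSC0ZZ and 0TSC4ZZ.

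The Re-Operation row of the same table lists the same operations as outcome events. Bulking appears as "Bulking Injection CPT 51715, ICD 9/10 59.72/ PCS 3E0K3GC" and open urethropexy as "Abdominal Retropubic Urethropexy CPT 51840,51841". Laparoscopic urethropexy, needle bladder neck suspension (CPT 51845) and Kelly plication (CPT 57220) also have CPT codes only.

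Three other places bear on this. Section 8.1 states that ICD-9/10 procedure codes as well as CPT are available across all sites. Section 7 defines the primary re-operation outcome by mid-urethral sling, bulking agent, bladder neck pubovaginal sling and revision for mesh exposure; it names neither urethropexy nor Kelly plication. The procedure reference list at the end of Section 13 gives "59.72/ 3E0K4GC Injection of implant into urethra and/or bladder neck", with no other ICD-10-PCS code for that operation.

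**The concern.** One operation is recognised by a wider set of codes when it is the index surgery than when it is the outcome. A record of 59.5, 0TSD0ZZ or 3E0K4GC with no CPT code can place a woman in the cohort, yet an identical record later in her follow-up is not an event under the written list.

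Re-operation is the first primary outcome in Section 7, and re-operation for SUI is a stated outcome in the synopsis and in Section 3. Under-counting would lower the reported rates and remove events from the re-operation risk model. Section 6 has one site write the transformation code from the common data model, so a gap in the list would be carried to every site.

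The omission does not look deliberate. The Re-Operation row describes itself as CPT-based, but it uses ICD-10-PCS codes for removal and revision and ICD codes for bulking. No text explains why the other operations lack them.

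**Working it through.** The protocol gives no figure to reproduce; the check is a comparison of code sets. A leading letter O in an ICD-10-PCS code is read as zero.

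**Step 1. Codes in the exposure row.**
CPT: 51715, 51990, 51992, 51840, 51841, 51845, 57220 = 7.
ICD-9 procedure: 59.72, 59.5, 59.3 = 3.
ICD-10-PCS: 3E0K3GC, 3E0K4GC, 0TSD0ZZ, 0TSD4ZZ, 0TSC0ZZ, 0TSC4ZZ = 6.
Distinct ICD procedure codes: 3 + 6 = 9.

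**Step 2. Codes carried into the Re-Operation row.**

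| Operation | CPT carried | ICD carried | ICD codes missing |
|---|---|---|---|
| Bulking | 1 of 1 | 2 of 3 | 3E0K4GC |
| Laparoscopic urethropexy/sling | 2 of 2 | 0 of 3 | 59.5, 0TSD0ZZ, 0TSD4ZZ |
| Open urethropexy | 2 of 2 | 0 of 3 | 59.5, 0TSD0ZZ, 0TSD4ZZ |
| Vesical neck suspension | 1 of 1 | 0 of 3 | 59.5, 0TSD0ZZ, 0TSD4ZZ |
| Kelly plication | 1 of 1 | 0 of 3 | 59.3, 0TSC0ZZ, 0TSC4ZZ |
| All, distinct | 7 of 7 | 2 of 9 | 9 − 2 = 7 |

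**Step 3. Which missing codes touch Section 7.** Bulking is named there, so 3E0K4GC is a gap on either reading. The other 7 − 1 = 6 codes are listed in the exposure row under urethropexy, neck suspension or Kelly plication, which Section 7 does not name. They matter to the primary outcome only if the appendix row governs.

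**Step 4. Codes with conflicting meanings.** The exposure row assigns 0TSC0ZZ and 0TSC4ZZ to Kelly plication (59.3). The closing reference list assigns both to paraurethral suspension (59.6), and 0TSC4ZZ also to suprapubic sling (59.4). They cannot simply be copied across.

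**Step 5. Scale, by assumption only.** Let s be the share of re-operations that are urethropexy, neck suspension or Kelly plication, and f the share of those recorded by ICD procedure code alone. Then observed risk = true risk × (1 − s × f). The protocol gives neither s nor f. The 5-year re-operation risk of 5.5% cited in Section 1.1 from a UK study serves only as a yardstick:

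- s = 5%, f = 5%: 5.5% × (1 − 0.0025) = 5.49%, a relative loss of 0.25%.
- s = 20%, f = 20%: 5.5% × (1 − 0.04) = 5.28%, a relative loss of 4%.
- s = 40%, f = 50%: 5.5% × (1 − 0.20) = 4.40%, a relative loss of 20%.

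The result runs from negligible to material and is fixed entirely by the assumed inputs.

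**Limit.** The extracted text is damaged just before the list of anti-incontinence operations in the Re-Operation row, so nothing is concluded about repeat sling codes. The entries compared above are legible.

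**The case against.** The strongest reply is that little may be lost. All seven CPT codes carry over and CPT is held at every site, so an operation is missed only when no CPT code was recorded. The protocol does not suggest that this is common. That stands: seven missing codes out of nine is a count of codes, and it says nothing about the share of events missed.

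Second, on Section 7's wording the only clear gap is one bulking code. This also stands, but it exposes a conflict that needs settling, because the appendix lists urethropexy and Kelly plication as re-operation events and the aims include re-operation for SUI.

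Third, each site reviews 50 to 100 charts, and the Mayo data are compared with a curated series. These checks might reveal missed re-operations, but they do not correct the list.

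Two stronger readings are tempting and are not supported:

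- A reader might infer that bulking too is found almost only by CPT. It keeps two of its three ICD codes.
- A reader might infer a larger loss in the non-mesh group, since those women can enter on ICD-only records while mesh women enter by CPT 57288. How the index operation was coded does not determine how a later one is coded, and the same outcome list applies to both groups: a mesh patient's ICD-only urethropexy is missed as well. Section 9.1 also rules out direct statistical comparison, although the rates will be shown side by side.

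**Conclusion.** The point holds as a coding inconsistency with a known direction and an unknown size. Under the written lists, urethropexy, neck suspension and Kelly plication are re-operations only when a CPT code exists, and bulking recorded solely as 3E0K4GC is not counted. Any loss lowers the re-operation rate.

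For bulking, the gap reaches the primary outcome on either reading. For the other operations, it does so only if the appendix row, and not the narrower wording of Section 7, defines the outcome. The documents support neither a numerical bias estimate nor a differential effect between groups. The correction is worth making because it is cheap and the codes are said to be available at all sites.

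**What to change.** 1. Reconcile Section 7 with the Re-Operation row by stating which anti-incontinence operations count as re-operation.
2. For each that counts, use the same CPT, ICD-9 and ICD-10-PCS codes as the exposure row. Add 3E0K4GC for bulking; 59.5, 0TSD0ZZ and 0TSD4ZZ for urethropexy and neck suspension; and 59.3 for Kelly plication.
3. Decide which procedure 0TSC0ZZ and 0TSC4ZZ denote, and apply that decision in the exposure row, the outcome row and the reference list.
4. Build the index-surgery, prior-SUI-surgery and re-operation flags from one shared procedure code table. De-duplicate by date, so that CPT and ICD records of one operation count once.

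The cost is an appendix edit and a small amount of coding. The reported re-operation rate may rise slightly.

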Next, if the characterization of the data is sufficient for the task, we will pursue a Cox proportional hazards model analysis, with each of the outcomes assessed from the time of the surgery as a time-to-event. We will censor the time-to-event analysis with death or loss to follow-up, defined as a time period >2 years from last applicable encounter of primary care, Obstetrics & Gynecology, or Urology. The models will first be developed at each institutional separately using LASSO Cox to predict time to event for each of the outcomes of interest. We will use the variables retained in any of the individual site models, and develop a Cox model using the method described by Lu and colleagues (WebDISCO) that uses a distributed analysis approach to obtain an exact model solution without sharing case level data (only intermediate and aggregate model coefficients and matrices)¹. This method is being used to protect patient data by processing it at the local institutions and only sharing intermediate modeling statistics (aggregates) between sites.

Because bootstrapping combined with the distributed analysis method would be computationally intensive, we will utilize 10-fold cross validation across all sites for internal validation of the risk model. We assessed overall discrimination using Harrell's concordance statistic (C-statistic). To provide calibration assessments, we will also evaluate the model at fixed time points of 1 year and 2 year for each outcome using the AUC and the Estimated Calibration Index (ECI). The ECI looks at the squared difference between the predicted probability and an estimated observed probability, ranging between 0 and 100, with 0 meaning perfect calibration. Additionally, we will graphically analyze calibration by investigating the smoothed observed-to-predicted probability plot.

Target Population:All women aged 18 or greater undergoing transvaginal surgery for stress
urinary incontinence with or without mid-urethral mesh sling implantation
are eligible for inclusion in the EHR data. Determination of the appropriate
mesh exposure during surgery will be determined through administrative
CPT procedure codes, as defined in the appendix. No exclusions will be
applied based on race or ethnicity. As a separate sensitivity analysis to
reduce potential lack of outcome ascertainment, we will exclude all
patients that do not also have continuity of care within the data site,

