4. STUDY DESIGN

This project will be a multi-site retrospective cohort analysis of trans-vaginally placed synthetic midurethral slings (MUS) implanted in patients for the indication of stress urinary incontinence for mid- and long-term outcomes (1 year and greater). We will identify all patients at each of the sites that have received a MUS through administrative and device implantation data. The key exposures will be MUS devices identified by administrative codes. Because ascertainment of the surgical approach is critical to the evaluation of post-operative complications, and has differing rates depending on the approach, we will determine which approach was used: Retropubic MUS (RPMUS), Transobturator MUS (TOMUS), Single-Incision Sling (SIMUS), or Adjustable Sling (AMUS). In prior work at Mayo, determination of the surgical approach was present in 100% of cases in the operative notes. We will also identify all patients that received a surgery for SUI without mesh (autologous or cadaveric fascial sling or burch colposuspension or bulking agents) and evaluate the same outcomes of interest in that population separately to provide an indirect comparison group. No direct comparison of mesh and non-mesh groups will be conducted. Patients with concomitant surgeries at the time of trans-vaginal mesh implantation for SUI will be included. The primary outcomes of interest are long-term safety outcomes relevant to these devices and defined in Section 7. In addition, using the Mayo Clinic data, we will be able to validate the electronic data with the manually curated data from 2010-2012². We will leverage this data to better understand how much of the data can be electronically generated and where additional information would need to be collected in an electronic environment.

Beyond the variables collected for exposures, outcomes, and cohort inclusion/exclusion, important covariates relevant to the device exposures and outcomes, and present prior to the surgery, will also be collected.

These include:

- Patient demographics
- Chronic pain
- Prior abdominal surgery
- Receipt of urodynamic testing (structured data will not have the results)
- BMI
- Insurance payer

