- Chronic clinical conditions will be aggregated using the Healthcare Cost and Utilization Project's Clinical Classification Software, which reduces all ICD-9/10 codes to 285 clinically meaningful groups⁴². The CCS has been updated to include ICD-10, which is important, as this project will span ICD-9 and 10 eras.
- Medication exposures will be aggregated using the PCORNet⁴³ instantiation of the RxNorm controlled vocabulary⁴⁴ and leveraging this vocabulary to the Anatomical Therapeutic Chemical (ATC) Level 4 groupings, which are clinically relevant drug classes.

Some co-variates may not be ascertainable in some participating sites' PCORNet CDM instances, and this will be explored and reported. Each of the outcomes, exposures, and covariates will be analyzed for counts in each site and a summarization and report will be provided to characterize the data at each site. Stratified reporting of those receiving surgery for SUI with mesh and those without mesh will be performed.

Next, if the characterization of the data is sufficient for the task, we will pursue a Cox proportional hazards model analysis, with each of the outcomes assessed from the time of the surgery as a time-to-event. We will censor the time-to-event analysis with death or loss to follow-up, defined as a time period

Version 2.0

[15 July 2020]

>2 years from last applicable encounter of primary care, Obstetrics & Gynecology, or Urology. The models will be executed at each institutional separately using LASSO Cox to determine the consistently included covariates in each institution⁴⁵. We will then use the final variable list and utilize the method described by Lu and colleagues that uses a distributed analysis approach to obtain an exact model solution without sharing case level data (only intermediate and aggregate model coefficients and matrices)⁴⁶.

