Insertion of mesh or other prosthesis for repair of pelvic floor defect 57267

General Prolapse Repair codes:

Repair of cystocele and rectocele, no graft 70.50 Repair of cystocele, no graft 70.51 Repair of rectocele, no graft 70.52 Other operations on cul-de-sac (repair of vaginal enterocele), no graft 70.92 Vaginal construction, no graft 70.61 Vaginal reconstruction, no graft 70.62 Vaginal suspension and fixation, no graft 70.77 Colpocleisis 70.80 Other uterine suspension 69.22 Vaginal repair of chronic inversion of uterus 69.23 Other repair of uterus and supporting structures 69.29 Other operation on supporting structure of the uterus 69.98 Obliteration of vaginal vault and total excision of vagina 70.4

General Prolapse CPT-4 Codes:

Rectocele repair 45560 Anterior colporrhaphy, repair of cystocele 57240 Posterior colporrhaphy, repair of rectocele 57250 Combined anteroposterior colporrhaphy with enterocele repair 57265 Combined anteroposterior colporrhaphy 57260 Synthetic Mid-Urethral Slings for Stress Urinary Incontinence in Women Protocol 1 Enterocele Repair—vaginal approach 57268 Enterocele Repair — abdominal approach 57270 Colpocleisis 57120 Colpopexy, vaginal, extraperitoneal approach 57282 Colpopexy, vaginal, intraperitoneal approach 57283 Insertion of mesh; vaginal approach 57267 Pereyra procedure, including anterior colporrhaphy 57289 Removal or revision of sling for SUI 57287 Revision (including removal) of prosthetic vaginal graft; vaginal approach 57295 Sling operation for SUI 57288 Uterine suspension 58400 Uterine suspension 58410 Vaginal hysterectomy, with repair of enterocele 58270 Vaginal hysterectomy, with colpourethrocystopexy, complicated 58293 Vaginal hysterectomy with repair of enterocele, complicated 58294

Sling Codes:

Retropubic Urethral Suspension 59.4, 59.71, 59.79 *Must be used concurrently with other prolapse repair codes.

International Classification of Diseases (ICD)-9/10 Diagnosis and Procedure Codes ⁵⁶

Diagnoses

Urinary incontinence	625.6/N39.3 Stress urinary incontinence, female
	599.82/N36.42 Intrinsic sphincter deficiency
	788.30/R32 Urinary incontinence, unspecified
	788.31/N39.41 Urge incontinence
	788.32/N39.3 Stress urinary incontinence, male
	788.33/N39.46Mixed incontinence (male) (female)
	788.34/N39.42 Incontinence without sensory awareness
	788.35/N39.43Post-void dribbling
	788.36/N39.44 Nocturnal enuresis
	788.37/N39.45 Continuous leakage
	788.38/N39.490 Overflow incontinence

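### The non-mesh definition accepts ICD-10-PCS 0TSC4ZZ, which the same appendix also maps to a suprapubic sling, so an ICD-10-era sling recorded without CPT 57288 would count as non-mesh

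*Protocol*

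**What the plan says.** The Data Collection table in Section 13 defines the two surgical groups with different kinds of code. The mesh row reads "Admin Codes CPT 57288" and lists nothing else. The non-mesh row gives each procedure a CPT, an ICD-9 and an ICD-10-PCS entry, and one of these is "57220/ 59.3/0TSC0ZZ, 0TSC4ZZ Kelly plication of urethrovesical".

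The procedure list that closes Section 13 has, in its sling group, "59.4/ OTSC4ZZ Suprapubic sling operation" and, in its group of other SUI procedures, "59.6/ OTSC4ZZ, OTSCOZZ Paraurethral suspension". A separate block of sling codes taken from a prior study reads "Retropubic Urethral Suspension 59.4, 59.71, 59.79".

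The synopsis (Target Population) says that mesh exposure is set by "CPT procedure codes, as defined in the appendix" and describes the comparator as women who had an SUI procedure without receiving mesh. Section 4 gives the intended content of the non-mesh group as "autologous or cadaveric fascial sling or burch colposuspension or bulking agents", and notes that "this project will span ICD-9 and 10 eras".

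**The concern.** One ICD-10-PCS code stands for a non-mesh procedure in the row that defines the group, and for a sling in the only other place where the Protocol interprets it. The two group definitions are also asymmetric: an ICD-10-PCS code can bring a woman into the non-mesh group, but only a CPT code can bring her into the mesh group. A sling that reaches the site's data through its ICD-10-PCS code alone would therefore land in the comparator.

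If such a sling is synthetic, any later erosion or removal is reported as an event after non-mesh surgery. This could happen only in the ICD-10 years, so the comparator's make-up could shift with calendar time. Section 9.1 plans to report the two groups side by side for indirect comparison, and that display is what would suffer.

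**Working it through.** The Protocol states no figure on this point, so the check compares code sets. Where the closing list prints a letter O in these codes it is read as a zero, as the same list prints for the neighbouring Burch codes.

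**Step 1: codes in the non-mesh row.** ICD-9: 59.72, 59.5, 59.3. ICD-10-PCS: 3E0K3GC, 3E0K4GC, 0TSD0ZZ, 0TSD4ZZ, 0TSC0ZZ, 0TSC4ZZ.

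**Step 2: compare with the closing list.**

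| ICD-9 | Label in closing list | ICD-10-PCS in closing list | ICD-9 in non-mesh row? | ICD-10-PCS in non-mesh row? |
|---|---|---|---|---|
| 59.4 | Suprapubic sling | 0TSC4ZZ | No | Yes |
| 59.79 | Pubovaginal sling and others | 0TQD3ZZ | No | No |
| 59.5 | Burch | 0TSD4ZZ, 0TSD0ZZ | Yes | Yes, both |
| 59.6 | Paraurethral suspension | 0TSC4ZZ, 0TSC0ZZ | No | Yes, both |
| 59.71 | Levator muscle operation | 0TUC0KZ | No | No |
| 59.72 | Injection of implant | 3E0K4GC | Yes | Yes |

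Two lines change status between coding systems: 59.4 and 59.6 are outside the non-mesh row in ICD-9 and inside it in ICD-10-PCS. None of the three codes in the sling-code block (59.4, 59.71, 59.79) is in the row.

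**Step 3: apply the definitions to a record.**

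- CPT 57288 present, with or without 0TSC4ZZ: mesh-exposed under the synopsis, and so outside the comparator.
- No 57288, ICD-9 59.4 only: meets neither exposure row.
- No 57288, ICD-10-PCS 0TSC4ZZ only: meets the non-mesh row. The operation could be a Kelly plication (as the row intends), a paraurethral suspension (absent from the row's ICD-9 codes), a fascial sling (wanted there by Section 4) or a synthetic sling (wrongly placed). The code does not say which.

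**Step 4: size.** If m synthetic slings enter by the third route and N women are correctly in the non-mesh group, the misclassified share is m/(N + m). The documents give neither m nor N. The site volumes in the synopsis (for example 6,106, 5,413 and 887) come from a query for CPT 57288. Every woman counted there has that code and falls under the first case, so no fraction of those volumes estimates m. With m = 0 the share is 0.

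**The case against.** The strongest reply is that the synopsis already settles exposure. Mesh status is set by CPT, and the comparator is women who did not receive mesh, so a woman with 57288 cannot be non-mesh whatever else is coded. That stands. A reader might infer that women carrying both codes are left unassigned, and the Protocol does not support that. It does not dispose of a record without 57288, because the synopsis refers to the appendix for the definition and the non-mesh row there prints ICD-10-PCS codes as qualifying codes.

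Other points also carry weight:

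- **CPT availability.** Section 8.1 lists CPT among the data available at all sites, and each site found its slings by CPT. Slings without 57288 may be few or none.
- **Sling is not mesh.** Section 4 deliberately places fascial slings in the non-mesh group. A reader might infer that every sling caught by 0TSC4ZZ is a misplaced mesh patient. Some would be correctly placed.
- **Status of the closing lists.** They are reference lists from prior work, and the one at issue gives the code to 59.6 as well, so the code is not specific to slings even there. It is nevertheless the Protocol's own reading of the code, and it conflicts with the exposure row.
- **ICD-9 was not perfectly clean.** The non-mesh row already admits a laparoscopic sling (CPT 51992, paired with 59.5). The contrast between eras holds for the listed sling codes, not for all slings.
- **Chart review.** Each site will review 50 to 100 cases covering exposures, which might reveal the problem. The review is not directed at this group, and Section 8.1 pulls peri-operative notes only for mesh cases.

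The Kelly plication entry breaks off mid-phrase in the text available, so a qualifying note after it cannot be excluded.

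**Conclusion.** The point holds in a limited form. The non-mesh row and the closing list give 0TSC4ZZ incompatible meanings. Because mesh is defined by CPT 57288 alone, an ICD-10-era sling recorded with 0TSC4ZZ and no 57288 would be counted as non-mesh without any way to tell synthetic from fascial.

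No size can be given. A reader might take a percentage of the sling volumes in the synopsis as the number misplaced. Those women were counted by 57288 and are not the ones at risk, and the frequency of 0TSC4ZZ without 57288 is nowhere stated.

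Nor does this reach the study's modelling. Sections 4 and 9.1 rule out a direct mesh versus non-mesh comparison, and the prediction model in Section 3 is for mesh recipients. What is exposed is the set of descriptive non-mesh rates shown beside the mesh rates.

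The conclusion assumes that the ICD-10-PCS entries in the non-mesh row are meant to operate. If only CPT is meant, they have no effect and should be deleted.

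**What to change.** Do not let 0TSC4ZZ on its own place a woman in the non-mesh group. Either of two edits would do:

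1. Identify Kelly plication by CPT 57220 or ICD-9 59.3 only.
2. Keep 0TSC4ZZ, but accept it only when 57288 is absent and the operative note confirms a non-mesh procedure, including a fascial sling as Section 4 intends.

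Then reconcile the non-mesh row with the closing procedure list, including 59.6 and its second code 0TSC0ZZ. State whether the synopsis rule that CPT sets mesh exposure means that the ICD-10-PCS entries are inactive.

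The cost is an edit to the code list before the shared transformation code goes to the sites. Under the first option a few Kelly plications recorded only as 0TSC4ZZ are lost. Neither Section 4 nor Section 6 names that procedure in the comparator, so the loss is small. Under the second option, note extraction, now limited to mesh cases, must be extended to these few records.
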